3.2.1. Confirmatory Factor Analysis using Phase 3 Data

A confirmatory factor analysis was completed using blinded data from one third of phase 3 patients. The acceptance criteria of the confirmatory factor analysis were prespecified as a Goodness of Fit Index > 0.90 and a Comparative Fit Index > 0.90 , a root mean square error of approximation < 0.06 and a non-significant p-value to show that the null-hypothesis that the data fits the three-factor model was not rejected (Table 3.2-1).

Factor loadings for the seven-item three-factor model supported the three-factor solution proposed by the exploratory factor analysis in the above described analyses using phase 2 data. Results indicated that the three-factor model, excluding item 8, had a Goodness of Fit Index and a Comparative Fit Index of 1.00 and a root mean square error of approximation of 0.00 (90% CI = 0.00-0.02). The test of model fit returned a p-value of 0.9394. The null hypothesis that the data fit the model was not rejected (see Table 3.2-1). Under this model, Item 5 (Feeling Tightness or Pressure in Pelvis) also cross-loaded onto Factor 2, assessing urinary symptoms.

Table 3.2-1: Confirmatory Factor Analysis of the UFS-QoL Symptom Severity Scale without Item 8: Model Fit Statistics at Baseline (MVT-601-3001 and -3002)

Model Fit Statistics^a				
Model	CFI	RMSEA (90%CI)	GFI	P-value
3-Factor Model (7-item)	1.000	0.000 (0.00-0.02)	1.000	0.9394
Factor Loading^b				
		Factor1	Factor2	Factor3
Q1	Heavy bleeding during your period	0.7314	0.2672	0.2024
Q2	Passing blood clots during your period	0.7620	0.1503	0.2099
Q3	Fluctuation in duration of menstruation	0.3263	0.1861	0.6909
Q4	Fluctuation in length of monthly cycle	0.1689	0.1561	1.0323
Q5	Feeling tightness or pressure in pelvis	0.4644	0.4657	0.1965
Q6	Frequent urination in daytime	0.2503	0.7727	0.1300
Q7	Frequent night time urination	0.1553	0.8605	0.1538

Abbreviations: CFI, comparative fit index; CI, confidence interval; GFI, goodness of fit index; RMSEA, root mean square error approximation.

^a Model fit statistics allow for assessment of the model appropriateness.

^b Rotation Method: Orthogonal.

In order to further assess the performance of the Fatigue item, which was excluded following the exploratory factor analysis due to cross-loading, the confirmatory factor analysis was reconducted with the inclusion of this item in Factor 1. Results showed that the eight-item three-factor model had a Goodness of Fit Index of 0.996, a Comparative Fit Index of 1.00 and a root mean square error of approximation of 0.00 (90% CI = 0.00-0.05). The test of model fit returned a p-value of 0.8056. However, the results for Item 8 showed a cross-loading of this item at 0.417 on Factor 1 and 0.437 on Factor 2 (Table 3.2-2). This continued cross-loading supports the exclusion of this item in the scoring of any factor (Table 3.2-2).

Table 3.2-2: Confirmatory Factor Analysis of the UFS-QoL Symptom Severity Scale with Item 8 included: Model Fit Statistics at Baseline (MVT-601-3001 and 3002)

Model Fit Statistics^a				
Model	CFI	RMSEA (90%CI)	GFI	P-value
3-Factor Model (8-item)	1.000	0.000 (0.00-0.05)	0.996	0.8056
Factor Loading^b				
		Factor1	Factor2	Factor3
Q1	Heavy bleeding during your period	0.732	0.265	0.211
Q2	Passing blood clots during your period	0.750	0.150	0.226
Q3	Fluctuation in duration of menstruation	0.296	0.175	0.767
Q4	Fluctuation in length of monthly cycle	0.180	0.167	0.932
Q5	Feeling tightness or pressure in pelvis	0.473	0.465	0.206
Q6	Frequent urination in daytime	0.251	0.757	0.137
Q7	Frequent night time urination	0.150	0.876	0.156
Q8	Feeling fatigued	0.417	0.437	0.136

Abbreviations: CFI, comparative fit index; CI, confidence interval; GFI, goodness of fit index; Q, question; RMSEA, root mean square error of approximation.

^a Model fit statistics allow for assessment of the model appropriateness.

^b Rotation Method: Orthogonal.

3.3. Classical Test Theory Psychometric Analyses of the Bleeding and Pelvic Discomfort Scale Based on Phase 3 Data

Each of the above-described factor analyses showed that a seven-item three-factor solution was appropriate for the UFS-QoL Symptom Severity Scale. Following this confirmation, blinded psychometric appraisal of the measure was implemented to further understand the performance of the items and subscales of the UFS-QoL Symptom Severity Scale. For the item level analysis, all items were assessed. For subscale level analysis, the analysis was focused, primarily, on the evaluation of the Factor 1 – the Bleeding and Pelvic Discomfort (BPD) Scale. The BPD Scale was selected as the primary focus for further psychometric evaluation, as it presents clinical and patient-reported symptoms proximal to the disease and is associated with high symptom burden experienced by most patients.

Analyses were based on pooled, blinded data from the first one third of patients enrolled in the two phase 3 studies of relugolix in UF (MVT-601-3001 and MVT-601-3002) who completed the PGA for symptoms and the UFS-QoL at Baseline and at Week 24. Of note, for the analyses specified in this section, only data at Baseline and Week 12 were used.

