Of note, in the TAK-385/CCT-001 phase 2 study, the UFS-QoL with a one-month recall period was applied, whereas the UFS-QoL with a three-month recall period is used in the phase 3 studies (MVT-601-3001 and MVT-601-3002). Therefore, confirmatory factor analysis and final psychometric testing of the chosen factor was conducted using blinded phase 3 data (see [Section 2.2](#)).

Exploratory Factor Analysis

The exploratory factor analysis was done on phase 2 data to identify the underlying constructs by the most parsimonious factor structure of the eight items in the Symptom Severity Scale.

Identification of the number of factors was based on the following criteria:

- Items with primary factor loading > 0.4 ;
- Factors with large eigenvalues considered as common factors using Kaiser criterion ([Kaiser, 1960](#)).

A scree plot was used as a supplemental tool to decide on the number of factors in the final model.

Confirmatory Factor Analysis

Once the number of factors was identified, a confirmatory factor analysis was conducted using blinded, pooled phase 3 data to confirm the factor structure. Only patients who completed the Baseline and Week 24 PGA for symptoms and UFS-QoL assessments were included in this analysis. Model fit was assessed based on the following:

- The goodness of fit as measured by χ^2 and Goodness of Fit Index; a Goodness of Fit Index > 0.9 is considered acceptable;
- The Comparative Fit Index was used to determine the acceptability of the model fit of the discrepancy function adjusted sample size; a Comparative Fit Index > 0.9 ([Hu, 1995](#)) was considered an acceptable fit;
- The root mean square error of approximation was used to determine the acceptability of model fit of the square root of the discrepancy between the sample covariance matrix and the model covariance matrix; the root mean square error of approximation had to be < 0.06 ([Browne, 1993](#)) to be considered an acceptable fit;
- P-value > 0.05 .

Once the final factor structure was identified, the factor reflecting items proximal to uterine fibroids and experienced by almost all patients with uterine fibroids were selected for further evaluation. Of note, this was the BPD Scale.

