3.4. Conclusions

The exploratory factor analysis offered support for a three-factor solution, which included factors assessing Bleeding and Pelvic Discomfort, Urinary Symptoms, and Fluctuation in Menstruation. The Fluctuations in Menstruation factor had an eigenvalue < 1 but had items that loaded at greater than 0.40 and made theoretical sense as a construct.

The exploratory factor analysis showed that Item 8, measuring fatigue, cross-loaded on two factors (Bleeding and Pelvic Discomfort and Urinary Symptoms). Since fatigue is a multidimensional concept that can assess impacts and/or symptoms concurrently, it was not included in the final factor structure. Confirmatory factor analysis on the seven-item three-factor solution provided support for the exploratory factor structure; however, Item 5 cross-loaded between the BPD and Urinary Symptoms factors in this analysis. As Item 5 (Feeling Tightness or Pressure in Pelvis) is a proximal symptom of uterine fibroids, this item was retained as part of the BPD factor.

To ensure that fatigue was not being inappropriately excluded from the three-factor structure, an additional confirmatory factor analysis was conducted with fatigue included within the BPD factor. The inclusion of fatigue in this model continued to show the expected cross-loading of this item. This analysis confirmed that the multidimensional concept of fatigue was not suitable for inclusion in the BPD factor.

The BPD factor, which assesses symptomology most proximal to the disease, was further assessed through classical test theory psychometric evaluation. The results showed that the items of the BPD Scale work cohesively to inform the total score of the measure, and adequately distinguish between severities. At a score level, descriptive statistics were able to support the construct validity and responsiveness of the BPD Scale through showing a monotonic improvement in BPD Scale score in line with patient self-reported improvement on the PGA (symptoms). Additionally, by showing that the items of the BPD Scale perform well together, the psychometric results help to further support the inclusion of the cross-loading Item 5 on the BPD Scale.

APPENDIX 4. APPROACH TO ESTIMATING THE RESPONDER THRESHOLD OF THE UFS-QOL BLEEDING AND PELVIC DISCOMFORT SCALE

The Uterine Fibroid Symptom and Health-Related Quality of Life Bleeding and Pelvic Discomfort (UFS-QoL BPD) Scale includes the following items:

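### The factor analysis called confirmatory in Appendix 3 is an unrestricted model with an improper solution; the published loadings support the three-factor structure only if Item 5 may load on both the bleeding and the urinary factor

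*SAP*

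**What the plan says.** Appendix 2, Section 2.1 sets out a two-step plan: find the factor structure of the eight symptom items in phase 2 data, then confirm it in blinded pooled phase 3 data. Four acceptance criteria are given: GFI above 0.9, CFI above 0.9, a p-value above 0.05, and "the root mean square error of approximation had to be < 0.06". Section 3.2.1 of Appendix 3 repeats them, including "a root mean square error of approximation < 0.06 and a non-significant p-value".

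The structure to be confirmed is Q1, Q2, Q5 (the BPD scale); Q6, Q7 (urinary symptoms); and Q3, Q4 (menstrual fluctuation). Section 3.2.1 states the result as: "Factor loadings for the seven-item three-factor model supported the three-factor solution proposed by the exploratory factor analysis". Table 3.2-1 reports CFI 1.000, GFI 1.000 and a "root mean square error of approximation of 0.00 (90% CI = 0.00-0.02"), and the text adds: "The test of model fit returned a p-value of 0.9394". The same table lists a loading for all seven items on all three factors, with an orthogonal rotation.

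On Item 5 the SAP is open: "Under this model, Item 5 (Feeling Tightness or Pressure in Pelvis) also cross-loaded onto Factor 2, assessing urinary symptoms". Section 3.4 keeps the item as a symptom proximal to uterine fibroids. Item 8 (fatigue) was added in a second run, and of it the SAP says: "This continued cross-loading supports the exclusion of this item in the scoring of any factor". Section 3.4 then concludes: "Confirmatory factor analysis on the seven-item three-factor solution provided support for the exploratory factor structure".

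**The concern.** A confirmatory model tests item assignment by fixing cross-loadings to zero, and it has no rotation to choose. A table with all loadings estimated and then rotated describes an exploratory model fitted a second time. Its good fit says that three factors reproduce the correlations. It says nothing against Q5 belonging with the urinary items, because the model allows every item to load anywhere.

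Change in BPD score is one of the seven alpha-protected key secondary endpoints and is marked in Table 1 as not listed in the protocol. Section 7.4.4.2 sends the reader to Appendix 3 for its derivation and validation, and the results go into the patient-reported outcome dossier. If the analysis could not have refuted the scoring, the statement that it confirmed the scoring is wrong as written.

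**Working it through.** **1. Which model produced the published fit?** For k items and 3 factors, an unrestricted model has ((k − 3)² − (k + 3))/2 df: 3 for k = 7 and 7 for k = 8. A restricted model with correlated factors and one factor per item has 28 − (7 + 7 + 3) = 11 df, or 36 − (8 + 8 + 3) = 17 df. Convert each stated p to chi-square, then take F = chi-square/259 and GFI ≈ k/(k + 2F), with the RMSEA limit from the noncentral chi-square (n = 260).

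| Model | df tried | chi-square | GFI | RMSEA upper limit | SAP reports |
|---|---|---|---|---|---|
| 7 items, p = 0.9394 | 3 | 0.404 | 0.9996 | 0.023 | 1.000; 0.02 |
| | 11 | 4.82 | 0.995 | 0.014 | |
| 8 items, p = 0.8056 | 7 | 3.77 | 0.996 | 0.048 | 0.996; 0.05 |
| | 17 | 11.9 | 0.989 | 0.036 | |

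The published figures are reproduced on 3 and 7 df and not on the restricted df. Section 3.2.1 says Item 8 was placed in Factor 1, yet Table 3.2-2 shows it loading on all three, which agrees with this.

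**2. Improper solution.** Q4 in Table 3.2-1: 0.1689² + 0.1561² + 1.0323² = 0.0285 + 0.0244 + 1.0656 = 1.119. With standardised loadings the unique variance is −0.12. Table 3.2-2 does not have this problem (0.180² + 0.167² + 0.932² = 0.929).

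**3. Rebuilding the correlations.** Multiply the Table 3.2-1 loading matrix by its transpose and set the diagonal to 1. For Q1, Q2, Q5 this gives r = 0.640, 0.504 and 0.465. As a check, use the baseline SDs 0.95, 1.09 and 1.18 from Table 3.3-2. Its third column is headed Q3, but its mean of 3.59 is that of Q5 in Table 3.3-1: 934/260 = 3.59. The item variances sum to 3.483 and the total-score variance is 7.135, so alpha = 1.5 × (1 − 3.483/7.135) = 0.768, as the SAP reports. Item-total correlations come out at 0.665, 0.625 and 0.533 against the reported 0.670, 0.620 and 0.533.

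**4. Restricted fits** (maximum likelihood, correlated factors, n = 260):

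| Structure | chi-square (df) | p | RMSEA | CFI | GFI |
|---|---|---|---|---|---|
| Q5 on BPD only, as scored | 34.1 (11) | 0.0003 | 0.090 (90% CI 0.057–0.125) | 0.973 | 0.962 |
| Q5 on BPD and urinary | 7.0 (10) | 0.72 | 0 | 1.000 | 0.992 |

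For the first row, RMSEA = √[(34.1 − 11)/(11 × 259)] = 0.090. It fails p > 0.05 and RMSEA < 0.06, and passes CFI and GFI. To pass, chi-square would have to fall below 19.7 (p) and 21.3 (RMSEA). Freeing the one loading lowers chi-square by 27.1 on 1 df, so essentially all the misfit comes from Q5. In the second row Q5 loads 0.41 on BPD and 0.37 on urinary symptoms. All unique variances are positive in both fits.

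**5. Robustness.** With n = 255 the first fit gives p = 0.0004 and RMSEA 0.090; with correlations from Table 3.2-2 the result is the same. In 150 random perturbations of the matrix, sized to the published residual chi-square of 0.404, chi-square stayed between 31.3 and 38.5, p was at most 0.001, and RMSEA ran from 0.084 to 0.098.

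**The case against.** The best reply is that the failure appears only when Q5's urinary loading is forced to zero, and the SAP discloses that loading twice and gives a reason for keeping the item. This stands. A restricted model that allows the disclosed loading passes all four criteria. Q5's loading on BPD in that fit (0.41) is above the SAP's 0.40 rule and its urinary loading (0.37) is below it. Moving Q5 to the urinary factor alone fits worse than the scored structure (chi-square 40.8 against 34.1, both on 11 df). A reader might infer that the BPD structure has failed or that the scale is invalid; these results do not support that.

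Nor does the scale rest on this analysis alone. The three items came from separate phase 2 data. Alpha is 0.768 at baseline and 0.882 at Week 12, Q5's item-total correlations are 0.533 and 0.674, and mean BPD score rises with baseline symptom severity.

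A reader might also infer that Q8 was dropped for exactly what Q5 was forgiven. The phase 3 cross-loadings are indeed alike (0.417 and 0.437 for Q8; 0.4644 and 0.4657 for Q5). But Q8 also missed the phase 2 threshold (0.399), while Q5 met it (0.467), and Section 3.4 adds a content reason for leaving fatigue out.

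The refit is approximate. It starts from loadings of an improper solution with Q4's diagonal reset to 1, and it assumes normal-theory likelihood for five-point items. The RMSEA interval reaches just below 0.06, although the SAP's criterion is read here on the point estimate.

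None of this answers the main point: the reported fit comes from a model that did not test the assignment of items, and disclosing the cross-loading does not make it a confirmation.

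**Conclusion.** The point holds as a wrongly stated analysis. The tables labelled confirmatory are unrestricted (3 and 7 df), the 7-item solution is improper without comment, and p = 0.9394 with RMSEA 0.000 is not evidence on which items form the BPD scale. On the rebuilt correlations the scored assignment misses two of the four stated criteria (p = 0.0003, RMSEA 0.090), and the three-factor structure is supported only if Q5 may belong to both the bleeding and the urinary factor. The degrees of freedom and the Q4 communality follow directly from the published tables. The refitted values rest on the implied matrix, n = 260 and maximum likelihood, and need the raw data to be exact.

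A reader might infer that the gated test of BPD change is compromised. It is not: the endpoint is a fixed sum of Q1, Q2 and Q5, the factor model used blinded pooled baseline data, and type I error is untouched. What changes is the strength of the structural evidence offered for the scale.

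**What to change.** - On the same 260 women, fit a restricted model with correlated factors, non-negative unique variances and stated df, once with Q5 on BPD only and once with its urinary loading free. Report both against the Appendix 2 criteria.
- Relabel Tables 3.2-1 and 3.2-2 as unrestricted (exploratory), state their df, and note the improper solution in the 7-item table.
- Restate Section 3.2.1, the opening of Section 3.3 and Section 3.4 to say that Q5 is retained on clinical and other psychometric grounds, and not because the factor analysis confirmed its place.
- Leave the alpha-protected endpoint and its position in the testing sequence as they are. A non-gated display of Q1 + Q2 and of Q5 separately would help attribute a BPD effect to bleeding or to pelvic pressure, but is optional.

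The cost is one rerun on data in hand, one extra table and some rewording. The downside is a less favourable fit statement in the patient-reported outcome dossier.

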3.3.1. Item Level Analysis of the UFS-QoL Symptom Severity Scale

UFS-QoL Symptom Severity Scale item responses were assessed for floor (highest possible severity) and ceiling effects (lowest possible severity). Overall, the measure showed no ceiling effects (response option 1, [Table 3.3-1](#), demonstrating that the items have scope to capture

patient improvement in disease burden. A greater proportion of patients responded at floor level (response option 5; range =11.15 to 36.15%), which is expected at the start of a clinical trial. All response options for all items were used, showing a good coverage of the range of disease burden. When considering BPD Scale items, all items showed a range of responses that covered the response scale, with over 50% of patients reporting being a (very) great deal distressed by heavy bleeding during menstrual period (Item 1), passing blot clots during menstrual period (Item 2), and feeling of tightness or pressure in the pelvic area (Item 5).

Table 3.3-1: Summary of UFS-QoL Symptom Severity Scale Response at Baseline by Items in MVT-601-3001 and 3002

Response	Q1 (N = 260)	Q2 (N = 260)	Q3 (N = 260)	Q4 (N = 260)	Q5 (N = 260)	Q6 (N = 260)	Q7 (N = 260)	Q8 (N = 260)
	n (%)							
1	4 (1.54%)	4 (1.54%)	44 (16.92%)	63 (24.23%)	21 (8.08%)	48 (18.46%)	54 (20.77%)	13 (5.00%)
2	15 (5.77%)	30 (11.54%)	48 (18.46%)	37 (14.23%)	24 (9.23%)	35 (13.46%)	53 (20.38%)	21 (8.08%)
3	53 (20.38%)	61 (23.46%)	66 (25.38%)	69 (26.54%)	57 (21.92%)	77 (29.62%)	64 (24.62%)	59 (22.69%)
4	101 (38.85%)	71 (27.31%)	64 (24.62%)	62 (23.85%)	96 (36.92%)	62 (23.85%)	55 (21.15%)	82 (31.54%)
5	87 (33.46%)	94 (36.15%)	38 (14.62%)	29 (11.15%)	62 (23.85%)	38 (14.62%)	34 (13.08%)	85 (32.69%)

Abbreviations: N, number of patients; n, number of patients in subset; Q, question.

3.3.2. Scale Level Analysis of the BPD Scale

3.3.2.1. Internal Consistency

Internal consistency was assessed for the BPD Scale at Baseline and Week 12. Reliability was acceptable at Baseline (> 0.70) and good at Week 12 (> 0.80 ; [Table 3.3-2](#)).

Table 3.3-2: Cronbach's Alpha Coefficient of BPD Scale by VISIT (MVT-601-3001 and 3002)

n		Q1	Q2	Q3	Alpha ^a
		Mean (SD)	Mean (SD)	Mean (SD)	
Baseline	260	3.97 (0.95)	3.85 (1.09)	3.59 (1.18)	0.768
Week 12	258	2.75 (1.47)	2.69 (1.46)	2.64 (1.36)	0.882

Abbreviations: n, number of patients; Q, question; SD, standard deviation.

^a Cronbach Coefficient Alpha

3.3.2.2. Item-to-Total Correlations

Item-to-total correlations were assessed to ensure that each item was associated with the BPD Scale score. Correlations demonstrate that each of the items have a strong relationship with the total score at Baseline and at Week 12 ($r > 0.50$) ([Table 3.3-3](#)). Correlations improved at Week 12, which represents a greater spread of the data across each item's five-point response scale, further supporting the relationship of these items to the BPD total score.

Table 3.3-3: Intercorrelation of Items in BPD Scale by Visit (MVT-601-3001 and 3002)

Question	Baseline N = 260	Week 12 N = 258
Q1	0.670	0.802
Q2	0.620	0.845
Q5	0.533	0.674

Note: Intercorrelation calculated using Pearson's correlations.

3.3.2.3. Item Discrimination Indices

An item discrimination index was employed to assess the ability of each item to discriminate between high and low severity patients. At Baseline, the discrimination index represents each item's ability to differentiate patients on the BPD Scale scores at a single time point, and at Week 12, the discrimination index represents the ability to differentiate patients based on their level of change from Baseline to Week 12 in the BPD Scale score.

Results show that all items had a discrimination index above 0.60, demonstrating that BPD Scale items are able to discriminate between high- and low-severity patients both when assessing single time point scores and change over time ([Table 3.3-4](#)).

Table 3.3-4: Item Discrimination Index of BPD Scale (MVT-601-3001 and 3002)

	Q1	Q2	Q5
Baseline (n = 260)	0.815	0.954	0.923
Week 12 (n = 258)	0.915	0.986	0.836

Abbreviations: n, number of patients; Q, question.

Note: BPD scale upper/lower ranges: Upper = at least 65-point reduction, Lower = at most 10-point reduction.

3.3.2.4. Known-Groups Validity

A known-groups analysis assessed the descriptive BPD score and score ranges for patients stratified by level of severity reported on the PGA (symptoms). Results from the known-groups validity assessment show that mean and median BPD Scale scores increase monotonically in line with PGA symptom severity (Table 3.3-5).

3.3.2.5. Ability to Detect Change

The BPD Scale's ability to detect change was assessed through the difference in BPD Scale scores over time in patients who have changed with respect to the measurement concept as measured by the PGA (symptoms). For each PGA stratified group, within person change from Baseline to Week 12 and standardized effect size statistics (SES) for change over the same period were assessed. SES statistics judged were based on Cohen's recommendations (small change, 0.20; moderate change, 0.50; large change, 0.80).

Results showed that the mean change for improving PGA categories had a monotonically increasing pattern from patients who had a PGA change of 0 to patients who had a PGA improvement of -4 (Table 3.3-6). Worsening groups (PGA change of +1 or +2) had very low levels of mean change, with wide standard deviations around the mean due to the low sample size in these categories.

In line with expectations, the SES statistics for the improvement categories (PGA score change of -1 to -4) were large (> 0.80) compared to the moderate SES found in the patients who reported no change (PGA score change of 0; SES = 0.55).

Table 3.3-5: Summary Statistics of BPD Scale Score at Baseline by PGA (symptoms) Response (MVT-601-3001 and 3002)

Baseline PGA	Baseline BPD Scale Score ^a						
	N	Mean	SD	Median	Q1, Q3	Min	Max
1	7	53.57	28.81	58.33	25.00, 75.00	16.67	91.67
2	21	59.92	26.56	58.33	41.67, 75.00	8.33	100.00
3	96	62.33	21.18	66.67	41.67, 75.00	8.33	100.00
4	89	75.09	19.48	75.00	66.67, 91.67	16.67	100.00
5	47	83.51	16.53	91.67	75.00, 100.00	41.67	100.00

Abbreviations: BPD, bleeding and pelvic discomfort; max, maximum; min, minimum; N, number of patients; PGA, Patient Global Assessment; Q1, first quartile; Q3, third quartile; SD, standard deviation.

a Transformed Score.

Table 3.3-6: Summary Statistics of Change from Baseline BPD Scale Score to Week 12 by PGA (symptoms) Change from Baseline (MVT-601-3001 and 3002)

PGA Change Category ^a	N	Mean	SD	95% CI	Median	Q1, Q3	Min	Max	Effect Size ^b
-4	23	-48.19	(42.27)	(-66.47, -29.91)	-66.67	-83.33, 0.00	-100.00	25.00	-2.93
-3	50	-49.33	(33.16)	(-58.76, -39.91)	-54.17	-75.00, -25.00	-100.00	33.33	-2.41
-2	74	-27.70	(30.75)	(-34.83, -20.58)	-25.00	-41.67, 0.00	-91.67	25.00	-1.25
-1	48	-23.09	(28.57)	(-31.39, -14.79)	-16.67	-33.33, -8.33	-100.00	33.33	-1.01
0	39	-10.68	(20.32)	(-17.27, -4.10)	-8.33	-25.00, 0.00	-66.67	33.33	-0.55
1	14	1.79	(19.11)	(-9.25, 12.82)	-4.17	-16.67, 8.33	-16.67	33.33	0.07
2	6	-1.39	(29.54)	(-32.39, 29.61)	-12.50	-25.00, 16.67	-25.00	50.00	-0.05

Abbreviations: BPD, blood and pelvic discomfort; CI, confidence interval; max, maximum; min, minimum; N, number of patients; PGA, Patient Global Assessment; Q1, first quartile; Q3, third quartile; SD, standard deviation.

Note: Statistics calculated using transformed score of BPD scale.

^a The PGA is a five-point, single item patient-reported outcomes tool that measures patient's symptoms. The PGA change category with -4 = Marked Improvement; 0 = No Change, +4 = Markedly Worse.

^b Standardized effect sizes are calculated as the mean divided by the standard deviation.

